CLINICAL STUDY PROTOCOL
Interventional Drug or Biologic

Varenicline for treatment of e-cigarette dependence

Protocol Number

2000032740

Protocol Version

9/20/2022

Version 5

PRINCIPAL INVESTIGATOR:

Name [name].
Department Psychiatry
[contact]
Email Address: [contact]

IND Number: N/A

IND Holder: N/A

NCT Number: Pilot study, not applicable

Study Phase (1, 2, 3, or 4-postmarketing): 1

Confidentiality Statement:

REVISION HISTORY:

Revision #	Version Date
Ver1	4.20.2022
Ver 2	5.2.2022-minor changes
Ver 3	5.23.2022
Ver 4	8.11.2022
Ver 5	9.20.2022
Ver 6	3/17/23

Synopsis

Primary Objective

The primary objective of this Phase 1 study is to determine whether varenicline reduces e-cigarette use in adults who regularly use e-cigarettes.

Secondary Objective (if applicable)

The secondary objective[s] of this study is] to determine whether varenicline promotes vaping cessation at week 12.

Study Duration

Participant duration in this study is 12 weeks. The entire study is expected to take about 2 year.

Study Design

Randomized, Placebo-controlled, double blind pilot study

Number of Study Sites

This is a dual site study that will be carried out at Yale and Medical University of South Carolina. The study will use remote/telehealth procedures, as much as possible, as detailed below

Study Population

This study will use various media outlets to recruit adults who report current e-cigarette use in South Carolina (for MUSC) and in Connecticut (for Yale). Advertising will target e-cigarette users who have a desire to quit and are willing to undergo treatment, set a quit date, and attempt to maintain e-cigarette abstinence. Mono-vapers will click the link in our Craigslist and social media ads which will open a screening survey through REDCap on their mobile devices. If the individual meets pre-screening eligibility, the research staff will call the participant to schedule an intake to confirm final eligibility for the study.

Number of Participants

We plan to enroll 40 participants across two sites. As with previous studies, we will make every effort to maximize participant retention via a thorough informed consent process, careful screening, and other practices.

Primary Outcome Variables

The primary outcome will be abstinence from vaping at week 8. Abstinence is defined as no vaping, not even a puff, every day for the last 7 days via self-report (i.e., 7 day point prevalent abstinence).

Secondary and Exploratory Outcome Variables (if applicable)

1.1 Introductory Statement

This document is a protocol for a human research study. The purpose of this protocol is to ensure that this study is to be conducted according to ICH GCP guidelines, and according to CFR 21 Part 312, other applicable government regulations and Institutional research policies and procedures.

2 Background

2.1.1 Preclinical Experience

Pharmacotherapy: Varenicline, an FDA-approved smoking cessation medication, functions as a partial agonist for the $\alpha 4\beta 2$ nicotinic receptor and is the most effective monotherapy for smoking cessation.¹⁻³ There is also persuasive evidence from a large clinical trial that varenicline is safe in a psychiatric population and does not increase the rate of suicidality or depression.¹ The American Thoracic Society (ATS) Clinical Practice Guidelines, the most recent comprehensive tobacco treatment guideline released in July 2020, suggests that varenicline should be prescribed as first line pharmacotherapy even in smokers who are not ready to quit.²¹ Currently there is minimal literature that addresses pharmacotherapy as a treatment option for vaping. This study will add to the literature on treatment options for adults who use e-cigarettes alone (mono-vapers). The participants will be given a dose titrated to 2mg daily which co aligns with the current FDA approved dose for smoking cessation.

2.1.2 Clinical Experience

We are using the same dose of the oral medication for vapers as we would for cigarette smokers. The participants will be given a dose titrated to 2mg daily which co aligns with the current FDA approved dose for smoking cessation.

Black-box warnings were removed by the FDA in recent years following the large clinical EAGLES trial showing that this is a low risk medication.¹ Additionally, meta-analyses have been conducted that show varenicline as a safe and useful medication.¹⁷⁻²⁰ Some side effects of varenicline include nausea, constipation, indigestion, abdominal pain, heartburn, increased or decreased appetite, trouble falling asleep or staying asleep, unusual dreams or nightmares, headache, lack of energy, back, joint, or muscle pain, and abnormal menstrual cycles.

2.2 Background/prevalence of research topic

The U.S. tobacco product landscape has changed dramatically within the last decade with the advent of new nicotine products, particularly electronic cigarettes (e-cigarettes).¹ While e-cigarettes were initially considered hopeful as a smoking alternative, they have shown to be less innocuous than previously believed. E-cigarettes are highly addictive,^{1, 3, 44} used commonly by youth,^{4,5} and are toxic to the lungs and circulatory system.^{6, 7, 47} In addition, most e-cigarette users commonly continue to smoke cigarettes, thus raising concerns about their ability to reduce tobacco-related harm.^{8-10, 11, 45}

Recent studies have shown that 20.7% of current combustible cigarette smokers that try e-cigarettes become dual users.⁴⁹ An increasing number of individuals are interested in quitting e-cigarette use and open to treatment for this purpose.⁴⁴⁻⁴⁸ Nevertheless, there is minimal literature on treatment options for e-cigarette addiction. There is a gap in research that does not address proper cessation methods for individuals who are mono e-cigarette users.

Varenicline is a highly efficacious FDA-approved smoking cessation pharmacotherapy. The aim of this study is to examine the effectiveness of varenicline for e-cigarette cessation medication for mono- e-cigarette use in combination with a minimal, self-guided behavior change booklet. This booklet will include general tips for e-cigarettes cessation and information about the free web-based e-cigarette cessation program sponsored by The Truth Initiative and Mayo called “This is Quitting”. This study will have an 8-week treatment period and a 4-week follow-up

phase. Participants will be randomized to receive an 8-week supply of varenicline or matching placebo (gel capsule filled with cellulose powder) in combination with the self-change booklet. We hypothesize that participants who receive varenicline will have higher rates of e-cigarette cessation.

Electronic cigarettes, also referred to as e-cigarettes, vaping devices, or vape pens, are battery-operated devices that heat and aerosolize a liquid solution that may contain nicotine and other additives such as flavors. Introduced to the U.S. in 2007, these devices were proposed as a potential harm reduction option for people who smoke combustible cigarettes. Indeed, there is some evidence that supports e-cigarettes for smoking cessation and tobacco-related harm reduction.⁹ Nevertheless, many smokers who try e-cigarettes to quit smoking are unsuccessful and become dual users of both products and among those who are successful quitting smoking, a number become dependent long-term e-cigarette users.¹⁰ The highly addictive nature of e-cigarettes, the potential toxicity to the body, and the minimal research on the long-term health effects of e-cigarettes present much risk to individuals who use e-cigarettes for smoking cessation.^{6, 7, 47} In the Tobacco Treatment Service at Smilow Cancer Hospital (for Yale) and in the Tobacco Treatment Program (at MUSC), we are now treating patients who quit smoking combustible cigarettes using e-cigarettes for their e-cigarette dependence. These patients used e-cigarettes to quit smoking but reported that they became more dependent on e-cigarettes than combustible cigarettes and expressed a desire to stop for health reasons. Data from recent reports provide support for our clinical experience and that most adults who use e-cigarettes exclusively (60%) plan to quit use of these products.²³

In the past decade, there has been a substantial increase in e-cigarette use in all adult age groups.¹⁷ A recent study⁵² shows that over 10% of the adult population in the US has tried e-cigarettes. At the same time, young people and never smokers also started using e-cigarettes, cohorts for whom these products were not intended.¹¹⁻¹² Between 2011 and 2014, e-cigarette use increased by 900% among U.S. middle and high school students and e-cigarettes have been the most commonly used tobacco product among U.S. youth since 2014.¹²⁻¹³ Several factors contributed to e-cigarette initiation among young people and never smokers including the availability of flavor products that are appealing to youth (e.g., candy flavors) and new technology that made it easier to use and conceal use from others.¹¹ Although these new products have been created to market to youth, adults have also succumb to this enticing marketing. This new technology also improved the nicotine delivery of these products, increasing their addiction potential. Earlier e-cigarette models did not deliver high nicotine levels to users.¹⁴ However, newer devices such as nicotine salt-based e-cigarettes (e.g., JUUL) more closely mimic combustible cigarettes by quickly delivering high levels of nicotine.¹⁴⁻¹⁵ In fact, a single JUUL pod contains as much nicotine as a pack of cigarettes.

Due to this rapidly evolving e-cigarette landscape, a new generation comprising never, former, and current smokers is now highly dependent on e-cigarettes and needs help. Tobacco product regulation and tobacco control policy cannot keep pace with this technology and are insufficient to address this new public health challenge. There has been minimal research on treatment for e-cigarette dependence; the limited focus has been on adolescents and young adults.

To address this significant gap, we propose to conduct a preliminary test of a highly effective FDA-approved smoking cessation pharmacotherapy (varenicline tartrate) for the treatment of e-cigarette dependence among adult mono- e-cigarette users coupled with a brief behavioral intervention, adapted for e-cigarette dependence, and informed by evidence-based behavioral techniques for smoking cessation. A case report of varenicline for e-cigarette cessation provide evidence for its potential efficacy.⁵³ Moreover, a clinical trial of varenicline for e-cigarette cessation is underway in adult dual users and adolescents.⁵⁴⁻⁵⁵ As more adults initiate vaping either for mono use or to quit smoking, e-cigarette dependence is

increasing. Yet, there is minimal scientific research on treatments for e-cigarette dependence. Our study aims to advance the science in this area.

3 Rationale/Significance

3.1 Problem Statement

As more adults initiate vaping either for mono use or to quit smoking, e-cigarette dependence is increasing. Yet, there is minimal scientific research on treatments for e-cigarette dependence. Our study aims to advance the science in this area.

3.2 Purpose of Study/Potential Impact

The purpose of this study is to understand if varenicline tartrate can help people stop or reduce vaping. Varenicline has been proven to reduce the desire to smoke cigarettes. With this study, we aim to test whether it shows a similar benefit for individuals who vape and are interested in quitting.

3.2.1 Potential Risks

The main study procedures include completion of questionnaires (minimal risk), varenicline use (use will be tracked as well as any new or recurring symptoms), and Truth Initiative texting services. This is a low-risk medication study (see text below). There is also a risk that the treatment the study participant is randomized to may prove to be less effective than the other study treatment or other available treatments (i.e., participants who receive placebo). We will conduct scheduled assessment throughout the intervention to review participant symptoms, mood, and wellbeing.

Breach of confidentiality: Study investigators across both sites have experience as an investigator dealing with such sensitive information and has experience assuring that data is adequately protected. Safeguards to protect confidentiality include locked records and firewalls around password-protected electronic data, and all study data being coded, with the key linking the code with a subject's identity being kept in a separate, locked file.

Assessments and Rating Scales: All assessments and rating scales are non-invasive and involve minimal risk to study participants.

Varenicline is an FDA approved smoking cessation medication. Black-box warnings were removed by the FDA in recent years following the large clinical EAGLES trial showing that this is a low risk medication.¹ Additionally, meta-analyses have been conducted that show varenicline as a safe and useful medication.¹⁷⁻²⁰ Some side effects of varenicline include nausea, constipation, indigestion, abdominal pain, heartburn, increased or decreased appetite, trouble falling asleep or staying asleep, unusual dreams or nightmares, headache, lack of energy, back, joint, or muscle pain, and abnormal menstrual cycles.

Other contraindications for varenicline include suicidal ideation.²¹ Suicidality will be assessed at prior to randomization and during the follow-up assessments. If an individual endorses suicidality during the pre-randomization screening, they will be marked as ineligible for the study. This will be assessed using the PHQ9 toolkit for suicide ideation (refer to assessments section). An alert is programmed into the REDCap system that if an individual indicates an active plan to either physically harm or kill themselves, an alert will be sent to the study team. They will then be contacted by our clinical team to complete a risk assessment over via phone. A member of the clinical team will query the participant for details regarding the suicidal ideation, including a likelihood of harming oneself imminently and a plan for committing suicide. If the participant reports an imminent likelihood of harming him/herself or a plan for committing suicide, the clinical team member will call emergency services and will remain on the phone with the participant until emergency services arrive. In the event that the participant expresses an imminent likelihood of harming him/herself, and

the connection is lost, emergency services will be contacted to provide emergency services with the participant's contact information, including address. If the participant is not in imminent danger, the clinical staff will provide referrals for local mental health resources and/or instruction to go to the ED or call 911 should suicidal ideation worsen. The clinical team member will suggest that the participant seek treatment and then will follow-up with the participant via phone one week later.

In the event that a participant endorses suicidal ideation but is not responsive to clinical staff's phone call within 48 hours, the participant will be emailed a list of local mental health resources and will suggest that the participant seek additional treatment. The email will also ask that the participant respond to the clinical staff either via phone or e-mail within 24 hours to confirm receipt of the treatment referrals. Should the participant not respond to the clinical staff's email within an additional 48 hours (4 days from completion of the assessment) and endorse "Several days", "More than half the days" or "nearly everyday" to "Thoughts that you would be better off dead or of hurting yourself in some way" on the PHQ9 suicidality toolkit at study screening, emergency services will be contacted and will be provided with the participant's name and address.

We will utilize the PHQ9 assessment to track depression and suicidal ideation during the baseline assessments. If suicidal ideation is endorsed, an automated "red flag" will be processed through our REDCap database. This red flag will indicate either a a) clinically significant increase in total PHQ scoring with an overall score of at least 15 (>5 point increase from baseline and resulting score >15), OR b) any value >0 for item 9/suicidal ideation). The red flag indicators will be monitored daily by our clinical team and will be met with the appropriate measures. These measures are based on prior MUSC-IRB approved protocols of varenicline (i.e., the STARS Pro00098479).

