Pharmacotherapy: Twenty participants will be randomized to receive active varenicline. Prior to randomization, the study physician, [name] or nurse practitioners from the Tobacco Treatment Service/PI [name] will conduct a pre-randomization medical review to ensure that they qualify for varenicline based on study eligibility criteria collected during primary (e.g., smoking history, age, medical history, and comorbidities) and secondary screening (psychiatric history, suicidal history, pregnancy status). A summary report that we create within our REDCap screening database, will be delivered electronically to study physician/nurse practitioners/PI [name]. They will review each participant's information and will determine whether to 1) accept the individual into the study, 2) reject the individual into the study (i.e., not eligible for varenicline), or 3) ascertain more information from the individual before either the decision to accept/reject the participant. The study physician/nurse practitioners may contact the individual to engage in further clinical interviewing of the potential participant. The disposition of each participant will be tracked within this screening database, allowing us to complete all CONSORT steps to study flow. The individual will not proceed to randomization and intake until we have signed, explicit documentation from the study physician/nurse practitioners/ PI [name] to do so. Thus, these procedures ensure that we retain physician/APRN oversight and approval of varenicline disbursement at the study outset. [name]/APRNs from the Tobacco Treatment Service retains their role in evaluation of adverse events as noted elsewhere within this application.

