A novel alert system will be built into the Adverse Event surveys REDCap database such that any severe adverse events (e.g., severe nausea, severe sleep disturbances, severe changes in mood) that are endorsed along with self-report of cessation of pharmacotherapy use will be monitored by research staff, who will consult with the study physician/APRN from the Tobacco Treatment Service/PI [name] when indicated for clinical assessment and management. We believe this alert system will improve varenicline medication adherence if the pharmacist/APRN/physician can quickly follow-up on any side effects that may be associated with pharmacotherapy use and call the patient with any recommended dose adjustments. All dose adjustments will be recorded in our REDCap database.

Guided Self-Change Pamphlet: All groups will receive this pamphlet as a brief behavioral component of the intervention. This 3-page pamphlet includes information on how to reduce and quit e-cigarettes on their own (on Page 1), how to prevent relapse to combustible cigarettes (for mono vapers who quit combustible cigarettes by vaping; on Page 2), and how to enroll in the online This is Quitting services (described above; on Page 3).

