6.1.3 Dosage, Administration, Schedule

Dose and schedule: We are using the same dose of the oral medication for vapers as we would for cigarette smokers. The participants will be given a dose titrated to 2mg daily which aligns with the current FDA approved dose for smoking cessation. The varenicline prescription will follow the standard induction period: varenicline 0.5 mg once per day for Days 1-3, varenicline 0.5 mg twice per day for Days 4-7, then varenicline 1 mg twice per day (when varenicline reaches peak efficacy for tobacco cessation). Participants will remain on varenicline for 8 weeks total. Dose adjustments (e.g., reduction to 0.5 mg twice per day if 1 mg is not well tolerated) will be allowed at the discretion of the clinical pharmacist/APRN/physician. The entire 8-week supply of varenicline will be shipped at week 1 according to the Pharmacy's workflow..

Medication Schedule: Both groups will follow the same medication schedule (listed below).

- Days 1-3: 0.5mg (or matching placebo) study pill once per day
- Days 4-7: 0.5mg (or matching placebo) study pill twice per day
- Weeks 2-8: 1mg or matching placebo) study pill twice per day

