6.2 Assessments

6.2.1 Efficacy

Study Assessments

The following tools will be used for the assessments conducted at baseline (week 0) and end of follow-up (Week 0, 8 & 12).

Demographics (Week 0): This questionnaire will collect basic demographic information for each subject including gender, ethnicity/race, employment status, etc.

Smoking/Tobacco Use History (Week 0): This will collect basic info about smoking and smoking cessation history, prior varenicline use, e-cigarette history, tobacco and nicotine product flavor preference, etc.

Modified Questionnaire on Smoking Urges (QSU) (Week 0, 8 & 12): This 3-item assessment is used to examine smoking related urges such as desire to smoke, anticipation of immediate positive outcome, etc.³¹E-cigarette Dependence (Week 0 & 8): The NIH Patient-Reported Outcomes Measurement Information System (PROMIS) measure for daily smokers has also been adapted to measure for use of other tobacco products.^{30, 40} This is a 4-item e-cigarette dependence questionnaire that measures withdrawal and craving.

E-cigarette Dependence Index (Week 0 & 8): This is a 10-item e-cigarette dependence questionnaire that measures difficulty quitting, withdrawal and cravings.⁵⁷

Subjective Effects Cigarettes and E-cigarettes (Week 0, Week 4): Participants will report on subjective evaluation about cigarettes and e-cigarettes. Subjective evaluation includes items derived from the Modified E-Cigarette Evaluation Questionnaire (meCEQ)⁵⁸ that have also been adapted for alternate tobacco products. It measures the degree to which participants experience reinforcing effects from smoking and e-cigarettes. The scale yields five clusters or domains: Smoking Satisfaction, Psychological Reward, Aversion, Enjoyment of Respiratory Tract Sensations, and Craving Reduction.⁵⁶

Patient Health Questionnaire-9 (PHQ9) (Week 0 and Bi-Weekly): which assesses for depression and includes an item on suicidal ideation.⁵⁰

Wisconsin Withdrawal Scale Brief (WSWS2-B): This 6-item scale assesses current symptoms of nicotine withdrawal including cravings and irritability.⁵⁹

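### Suicidal ideation bars entry as a contraindication, but a positive PHQ-9 item 9 on treatment requires no prescriber decision on study drug, and the last non-responder step is written only for screening

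*Combined protocol and SAP*

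**What the plan says.** Section 3.2.1 states: "Other contraindications for varenicline include suicidal ideation". The statement recurs in 5.1, in the Adverse Events paragraph of 6.1.3, and in 7.12. Anyone who endorses suicidality before randomization is ineligible. A physician, nurse practitioner or PI must also sign approval before randomization (5.1, 6.3). The protocol's summary of that review is that "we retain physician/APRN oversight and approval of varenicline disbursement at the study outset". The next sentence keeps the APRNs in the evaluation of adverse events.

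Suicidality is also measured after randomization. Section 6.2.1 lists "Patient Health Questionnaire-9 (PHQ9) (Week 0 and Bi-Weekly", and the table in 6.3.5 agrees. The written responses are:

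- **Plan alert.** "An alert is programmed into the REDCap system that if an individual indicates an active plan to either physically harm or kill themselves", the study team is notified and the clinical team makes a risk assessment by phone.
- **Red flag.** This is raised by any item 9 value above 0, or by a rise of more than 5 points to a total above 15. The clinical team checks flags daily. Its measures are not listed; they are said to be based on earlier approved varenicline protocols, with STARS cited.
- **Imminent danger or a plan.** Emergency services are called.
- **No imminent danger.** Referrals and emergency advice are given. "The clinical team member will suggest that the participant seek treatment and then will follow-up with the participant via phone one week later".
- **No answer to the call within 48 hours.** An email is sent. After a further 48 hours of silence, for a person who endorsed item 9 "on the PHQ9 suicidality toolkit at study screening, emergency services will be contacted".

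Outside this pathway, 5.1 says: "A novel alert system will be built into the Adverse Event surveys REDCap database". It covers severe events reported together with stopping the drug, and staff consult the physician, APRN or PI when indicated. Dose adjustments "will be allowed at the discretion of the clinical pharmacist/APRN/physician" (6.1.3). Investigators may withdraw anyone (6.3.7), and the PI leads a weekly review of participants and adverse events (7.11).

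**The concern.** The protocol treats ideation as a reason not to take varenicline, and it measures ideation in people who may be taking varenicline. The natural consequence is that a positive answer on treatment should reach someone with authority over the drug, who then decides. The written response covers crisis care and referral but stops short of that decision. Followed as written, a participant who develops ideation without hospitalization can go on taking capsules, in a state the protocol itself calls a contraindication, with no recorded judgement that this is acceptable.

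The non-responder wording adds a second problem. The strongest step is attached to people who have received no study drug, and as written it is not available for those who have.

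**Working it through.** The first three steps are a comparison of the text. The last is arithmetic on an assumed rate.

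**Step 1: the four copies of the pathway.**

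| Section | Prescriber named as recipient of a positive item 9 | Study drug decision stated | Final non-responder step |
|---|---|---|---|
| 3.2.1 | No | No | Tied to screening answers |
| 5.1 | No | No | Sentence breaks off before the step |
| 6.1.3 | No | No | Tied to screening answers |
| 7.12 | No | No | Tied to screening answers |

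**Step 2: other routes to a drug decision.**

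- APRN role in adverse event evaluation (5.1, 6.3): continues through the study, but applies only once the flag is treated as an adverse event, and the text does not say who decides that.
- Adverse Event survey alert (5.1): a different instrument. Read literally, it needs a severe event and self-reported cessation of the drug, so it misses a participant with item 9 above 0 who is still taking capsules.
- Dose discretion (6.1.3), withdrawal (6.3.7) and the weekly review (7.11): each permits action, but none requires a decision or mentions item 9.
- Serious event reporting (6.2.3): covers hospitalization, so the gap concerns ideation short of that.

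**Step 3: whom the last non-responder step covers.** The timing reproduces the plan's figure: 48 h + 48 h = 96 h = 4 days. The step applies to a person who gave one of the three listed frequency answers to item 9 at screening. If any of those answers counts as endorsing suicidality, that person is already ineligible. Everyone randomized then falls outside the clause as written, whatever they report later.

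**Step 4: size.** The documents give no rate of item 9 values above 0 on treatment. Let r be the assumed share of participants with at least one, with full follow-up. N = 40 enrolled and n = 20 on varenicline (5.1). Expected number = N × r; chance of at least one = 1 − (1 − r)^N.

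| r | Expected of 40 | Chance of at least one in 40 | Expected of 20 | Chance of at least one in 20 |
|---|---|---|---|---|
| 1% | 0.4 | 33.1% | 0.2 | 18.2% |
| 2% | 0.8 | 55.4% | 0.4 | 33.2% |
| 5% | 2.0 | 87.1% | 1.0 | 64.2% |
| 10% | 4.0 | 98.5% | 2.0 | 87.8% |

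The columns for 40 give the review load, because prescribers are blinded (6.1.5) and must assess every flag. The columns for 20 give the number exposed to the drug to which the contraindication applies. Both count any positive item 9, so they are upper bounds for ideation without hospitalization.

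**The case against.** The best defence is that a route exists without being spelled out. Section 6.1.3 places the pathway under an Adverse Events label, 6.2.3 refers back to adverse event procedures already described, the APRNs keep their role in evaluating such events, and prescribers have discretion over dose. The clinical team is undefined and may include a prescriber. Names are removed, so the people guiding relatedness review and leading the weekly meeting may be the people who approve varenicline. STARS may contain a drug-hold step. The protocol also describes varenicline as low risk and reports evidence that it does not increase suicidality, so clinical judgement is a defensible basis for a 40-person pilot.

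Much of this stands. It makes it plausible that a prescriber would be involved in practice. It does not turn a permitted decision into a required one, and two sites should not depend on an unwritten step here.

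A reader might infer three stronger points that the documents do not support:

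- **Prescriber oversight ends at randomization.** The sentence on adverse event evaluation says otherwise.
- **Ideation without a plan goes unnoticed because one alert needs a plan.** Any item 9 value above 0 raises the daily-checked flag, and the non-responder text implies a call for ideation generally.
- **Varenicline causes ideation.** Nothing here shows that. The point rests only on the protocol's own use of the word contraindication.

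The screening wording may be loose drafting. The same text ties PHQ-9 tracking to baseline, yet defines a rise from baseline. That makes an oversight likely, but staff follow the written words.

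**Conclusion.** The point holds in a limited form. The protocol bars entry for suicidal ideation and monitors it on treatment, but no written step requires a prescriber's study drug decision after a positive item 9. The last non-responder step, as written, does not cover participants on study drug.

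This is a gap in required procedure and not evidence that participants would in fact be left unassessed. It rests on the supplied text; the content of STARS and the makeup of the clinical team are unknown. At an assumed 1% to 10%, 0.4 to 4 of 40 participants would flag, of whom 0.2 to 2 would be on varenicline. The range is wide and cannot be narrowed from these documents. The case for change is that the correction is specific and nearly free.

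**What to change.** Amend 7.12 and its copies in 3.2.1, 5.1 and 6.1.3:

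1. Name the study physician or APRN as same-day recipient of every post-randomization item 9 value above 0. That person assesses the participant, records a continue, hold or stop decision, and tells the participant directly. The decision comes before any further shipment. Telling the participant matters because 6.1.3 and 6.3 ship all 8 weeks at once; 6.3.5 instead describes a second shipment at week 4.
2. Make the final non-responder step apply to an item 9 answer at any assessment, and complete the sentence that breaks off in 5.1.

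The cost is a few sentences, one REDCap routing rule, a small clinician review burden, and an occasional emergency contact for a silent participant who is not in danger. Holding study drug needs no unblinding. A descriptive by-arm count of participants with any on-treatment item 9 value above 0 in 6.4.2, and a rule on when a flag is coded as an adverse event, would be useful but are optional.
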